Sponsor	The sponsor is the party that commissions the organisation or performance of the research, for example a pharmaceutical company, academic hospital, scientific organisation or investigator. A party that provides funding for a study but does not commission it is not regarded as the sponsor, but referred to as a subsidising party.
TEI	Transforaminal Epidural Injection
TEIAS	Transforaminal Epidural Injection in Acute Sciatica
VAS	Visual Analogue Scale
WMO	Medical Research Involving Human Subjects Act; in Dutch: Wet Medisch-wetenschappelijk Onderzoek met Mensen

SUMMARY

Rationale: To study (cost) effectiveness of the transforaminal epidural injection with analgesic and anti-inflammatory medication (TEI) in order to relieve the symptoms and to evaluate the intervention as a predictor tool for symptoms of sciatica in the long term.

Objective: To evaluate the percentage of patients that experience satisfactory (long term) decrease in leg pain in the TEI group in comparison to the conservative care group.

Study design: Randomised controlled trial

Study population: Patients that suffer 3-8 weeks from sciatica (Numeric Rating Scale ≥ 6 , on a 10 point scale)

Intervention: transforaminal epidural injection with analgesic and anti-inflammatory medication

Main study parameters/endpoints: the percentage of patients that experience satisfactory decrease (NRS lower than 4) in leg pain after 2, 10 and 21 weeks after randomization in both treatment arms

Nature and extent of the burden and risks associated with participation, benefit and group relatedness: the participants fill in questionnaires at baseline, at 1, 2, 4, 10 and 21 weeks after randomization. Participants will also fill in cost-diaries during this period. TEI as an intervention tool is considered usual care for sciatica patients, though the timing of the injection is not clearly defined. The extent of risk from TEI is comparable to usual care.

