2. OBJECTIVES

Primary study objective:

To study effectivity of the epidural injection with analgesic and anti-inflammatory medication to relieve the symptoms within two weeks follow up.

It will be evaluated what the average leg pain score is in both treatment arms at two weeks follow up. It will be evaluated how long the effect lasts.

The leg pain and functionality at 4 weeks after randomization will also be evaluated to get informed on the responsiveness on TEI in a somewhat later stage.

Secondary study objectives:

To evaluate the outcome of TEI in the first two weeks after randomization as a predictor of NRS leg pain at 14-16 and ca 26 weeks after onset of leg pain.

Ideally, responsiveness to TEI can predict the clinical condition at 14-16 weeks after onset of sciatica. The hypothesis is that being non-responsive to TEI within two weeks, predicts an unsatisfactory condition after 14-16 weeks of suffering. This is the category of patients that in contemporary care in the Netherlands will be offered a surgical intervention. If our hypothesis is correct, in the future, this population of patients can be offered a surgical intervention at an earlier time point.

The ca 26-week time point is chosen since in the Sciatica trial [2], both the conservative and the surgical group demonstrated comparable outcome data.

Patients in this study are included while suffering from severe leg pain for 3-8 weeks.

Presumably most patients will enter the study with 4-6 weeks of leg pain. This means that on average 10 weeks after randomization, the 14-16 week leg pain time point is reached. This means that 21 weeks after randomization the ca 26-week leg pain time point is reached.

The response in NRS leg pain, ODI and patient satisfaction at 1 week after injection and at 2 weeks after injection will be correlated to the value of these parameters at 10 and 21 weeks after randomisation.

To evaluate the cost-effectivity of analgesic/anti-inflammatory epidural injections to relieve symptoms of early sciatica.

A substantial portion of the patients in this study will eventually have an MRI of the lumbar spine. These MRIs will be evaluated according to our standard MRI evaluation protocol, that has been proven to generate additional successful conclusions and subsequent publications in the past [10-15]. Protruding disc, disc and vertebral end plate changes (MODIC) will be correlated to clinical data.

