NRS leg pain that decreases below the value of 4 (on a 10 point scale) within two weeks after TEI is documented as successful effect of TEI. NRS leg pain that remains higher than a value of 4 at a time interval of two weeks after TEI makes a patient eligible for surgery if the patient requests for surgery. If surgery is requested by the patient (either in the control or intervention group), general guidelines for timing of surgery will be conducted, meaning that the patient is encouraged to postpone surgery till 14-16 weeks after onset of pain. This decision is made using Shared Decision Making and it is possible that the patient is operated before the 14-16 week time point. The patients who are randomized cannot be operated in the first two weeks after randomization, unless sudden loss of strength or a cauda equina syndrome is reported. We expect that during these two weeks TEI will have its effect. Four

weeks after randomization the outcome parameters are measured again to be informed on the late effect of TEI. Patients will be followed up for a total duration of 21 weeks starting from the moment of randomization. Questionnaires will be filled in at baseline, 1, 2, 4, 10 and 21 weeks follow-up. A schematic overview of the study procedures is outlined in figure 1. Note that this figure does not hold into account that it is possible for patients randomized to the treatment group to receive additional injections if necessary.

[figure not shown]

Fig.1 Flow diagram of study procedures

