4.4 Sample size calculation

We hypothesize that patients in the intervention group will have a mean NRS for leg pain of 4.0 on a 10-point scale at two weeks after treatment with TEI and patients in the control group will have a mean NRS for leg pain of 5.5 two weeks after randomization. A difference of 1.5 points on the NRS scale will be considered clinically relevant [17]. With a standard deviation of 2.6 (according to results of Joswig [18]), a power of 90% and a level of significance of 5% 64 patients are needed per group. This is a total of 128 patients. With a loss to follow-up of 10% we aim to include 142 patients.

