6. METHODS

6.1 Study parameters/endpoints

6.1.1 Main study parameter/endpoint

NRS leg pain: The pain intensity in the leg and the back will be measured with a 10-point horizontal Numeric Rating Scale (NRS), ranging from 0 (no pain) to 10 (worst imaginable pain). During each visit the NRS leg pain and NRS back pain will be scored. The patient is not entitled to see the pain scores indicated during previous visit(s). The NRS scores will be measured at baseline and at 1, 2, 4, 10 and 21 weeks after randomization.

The average score for NRS leg pain at two weeks after injection is compared to the average score for NRS leg pain in the prolonged conservative care group, 2 weeks after randomization. This will be calculated again at 4 weeks after randomization.

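### The plan names two primary endpoints: a percentage with NRS leg pain below 4 at 2, 10 and 21 weeks in the Summary, and mean NRS leg pain at 2 weeks in the body

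*Combined protocol and SAP*

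**What the plan says.** Summary. The objective is a proportion: "To evaluate the percentage of patients that experience satisfactory (long term) decrease in leg pain in the TEI group", compared with conservative care. The main endpoint is "the percentage of patients that experience satisfactory decrease (NRS lower than 4) in leg pain after 2, 10 and 21 weeks after randomization".

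Body. The primary objective in Section 2 is a mean at one time point: "It will be evaluated what the average leg pain score is in both treatment arms at two weeks follow up". It adds "It will be evaluated how long the effect lasts". Section 4.4 sizes the trial on a "mean NRS for leg pain of 4.0 on a 10-point scale at two weeks after treatment with TEI" against 5.5 in controls. Section 6.1.1, under the main-endpoint heading, states "The average score for NRS leg pain at two weeks after injection is compared to the average score for NRS leg pain" in the control group 2 weeks after randomisation, followed by "This will be calculated again at 4 weeks after randomization". Section 8.1 applies an unpaired t-test to mean NRS leg pain and repeats it at week 4, under the primary heading.

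Elsewhere. Section 3 records success of the injection (TEI) as "NRS leg pain that decreases below the value of 4 (on a 10 point scale) within two weeks after TEI". The cost-effectiveness paragraph of 8.2 equates symptom relief, counted in patients, with the primary outcome measure, but gives no threshold or time point.

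**The concern.** Both versions stand in current text. They differ in the type of variable (binary or continuous), in the time points (2, 10 and 21 weeks, or 2 weeks with a repeat at 4) and in the test they need. No sentence says which one governs.

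The trial is open-label and its main outcome is patient-reported, so a single pre-specified primary endpoint is an important protection against selective reporting. As written, an author could present either the responder result or the mean as planned. The Summary's 10- and 21-week endpoint also has no specified analysis, so the question of how long the effect lasts has no leg-pain comparison between arms after week 4.

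**Working it through.** **1. Side by side**

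| Place | Variable | Time | Comparison between arms |
|---|---|---|---|
| Summary, objective and main endpoint | % with NRS leg pain <4 | 2, 10, 21 weeks from randomisation | none in Section 8 |
| Section 2, primary objective | mean NRS leg pain | 2 weeks | see 8.1 |
| 4.4 | mean, 4.0 vs 5.5, SD 2.6 | 2 weeks (from TEI; from randomisation in controls) | basis of the 64 per arm |
| 6.1.1 and 8.1 | mean NRS leg pain | 2 weeks, repeated at 4 | unpaired t-test |
| Section 3 | NRS <4, TEI only | within two weeks after TEI | none |
| 8.2, cost-effectiveness | patients with symptom relief, undefined | not stated | net benefit only |

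The other tests in 8.2 do not fill the gap. The t-tests of change stop at week 4. The 2-week success data are used to predict later success. The chi-square tests of dichotomised Likert recovery concern a different outcome, and the text does not say outright that they compare arms.

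**2. The plan's own sample size**

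Inputs from 4.4: difference 1.5, SD 2.6, 5% significance, 90% power. Sidedness is not stated; two-sided reproduces the figure, while one-sided gives 52.

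n = 2 × (1.960 + 1.282)² × (2.6/1.5)² = 63.1, so 64 per arm. Noncentral-t power at 64 per arm is 89.9%. Total 128; 128/0.90 = 142.2, against the stated 142. The arithmetic is sound, and it belongs to the 2-week mean.

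**3. The same 64 per arm for NRS <4 at 2 weeks**

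The documents give no NRS <4 rates, so this step is illustrative. With a normal NRS and the plan's means and SD:

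- TEI: Φ((4 − 4.0)/2.6) = 50.0%. Control: Φ((4 − 5.5)/2.6) = 28.2%. The mean proportion p̄ is 0.391.
- Power = Φ{[|p₁ − p₂|√n − 1.960√(2p̄(1 − p̄))] / √(p₁(1 − p₁) + p₂(1 − p₂))} = Φ{[0.218 × 8 − 1.960 × 0.690]/0.673} = Φ(0.58) = 72.0%.
- n for 90% = (1.960 × 0.690 + 1.282 × 0.673)²/0.218² = 103.2 per arm.

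Other shapes with the same means and SD:

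| Assumed distribution | TEI vs control | Power at 64 | n per arm for 90% |
|---|---|---|---|
| Normal, cut 4.0 | 50.0% vs 28.2% | 72.0% | 103.2 |
| Normal, cut 3.5 (whole scores of 3 or less) | 42.4% vs 22.1% | 69.4% | 109.4 |
| Truncated normal 0–10, cut 4.0 | 54.1% vs 30.3% | 78.2% | 89.0 |
| Beta on 0–10, cut 4.0 | 53.5% vs 31.1% | 73.1% | 100.6 |
| Integer 0–10, two matched models | 44.2% vs 23.1%; 46.0% vs 23.9% | 72.2%; 75.2% | 102.7; 95.6 |

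The range is 69–78% power, with about 89–110 per arm needed for 90%.

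A cruder alternative borrows the 66% early response rate cited in the Introduction for the TEI arm. Power is then 94.8%, 84.7%, 67.0% or 44.9% for control rates of 35%, 40%, 45% or 50%.

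**4. How often the two week-2 results part company**

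Simulated trials with 64 per arm, 60,000 per scenario:

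- At the plan's effect, across a normal model (cut 4.0) and two integer models, the mean is significant and NRS <4 is not in 15.2–17.9% of trials; the reverse occurs in 1.3–1.8%. Together they disagree in about 17–19%. The normal model with cut 3.5 gives about 22% (21.0% + 1.3%).
- With no effect, at least one is significant in 7.4–8.3% of trials, against a nominal 5%.

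**The case against.** The strongest reply is that the operative sections agree. The objective, the sample size, the main-endpoint section and the primary analysis all use the mean, 6.3 speaks of a primary endpoint 2 weeks after randomisation, and 8.1 names one test. On that view the Summary is a synopsis out of step with the body, and anyone following 8.1 would not inflate the error rate. This is a good argument for which endpoint to keep, but it does not remove the conflict. The Summary is current text, the economic section also treats the primary outcome as a count of patients, and the Introduction argues that averaging over all patients can hide an effect in responders.

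It can also be said that the net-benefit analysis compares a responder outcome between arms by intention to treat. With relief undefined in threshold and time, it cannot stand in for a test of NRS <4. The Likert comparisons may well be meant between arms at 10 and 21 weeks, but they are not leg pain.

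Three points stand:

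- The responder power figures rest on assumed distributions. The 66% describes response within hours, so the range built on it carries little weight.
- The Section 3 success definition reads as a record of individual response, not a rival trial endpoint. The sentence after it, on eligibility for surgery, is a clinical rule and no part of this point.
- The 4-week repeat is described elsewhere as a later look, so it needs relabelling only.

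**Conclusion.** The contradiction is real and needs correcting: the endpoint headed as main in the Summary is neither powered nor tested in the body. That conclusion rests on the text alone. The 90% power claim is correct for the 2-week mean and for nothing else. For NRS <4 at 2 weeks, 64 per arm gives roughly 69–78% power if the plan's means and SD hold and the distribution is one of those tried. At the planned effect the two results would disagree on significance in about one trial in five or six. A free choice between them costs about 2 to 3 percentage points of type I error.

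A lesser related fault is the time origin. 4.4 and 6.1.1 count two weeks from injection in the TEI arm and from randomisation in controls, while 6.3 and the questionnaire schedule count from randomisation in both.

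**What to change.** 1. In both the objective and main-endpoint lines of the Summary, name mean NRS leg pain at 2 weeks as the single primary endpoint. Label the 4-week mean as secondary in 6.1.1 and 8.1.
2. State one time origin for both arms in 4.4, 6.1.1 and 8.1. The questionnaires already run from randomisation. On that origin, an injection given within 4 days is assessed 14 − 4 = 10 to 14 − 0 = 14 days later.
3. Make NRS <4 at 2, 10 and 21 weeks a named secondary endpoint, defined identically in both arms, and reconcile the Section 3 success definition with it as an outcome definition only. In 8.2, add the risk difference between arms with 95% CI at each of these times, and the difference in mean NRS leg pain with 95% CI at 10 and 21 weeks.
4. In the cost-effectiveness text, define symptom relief as NRS <4 at one stated time point and remove the clause that equates it with the primary outcome measure.
5. State in 4.4 that the 90% power refers to the 2-week mean only.

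The cost is a wording amendment and a few secondary analyses of data already scheduled, with no extra patients or visits. The price is that responder and long-term results become openly secondary, despite the Introduction's case for looking at responders. If the sponsor prefers the responder endpoint as primary, the plan must say so, give a single time point or a multiplicity rule, and recalculate the sample size.

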1. INTRODUCTION AND RATIONALE

Sciatica is a condition of radicular pain in the leg and is usually caused by herniation of a lumbar intervertebral disc. The herniated disc compresses a lumbar nerve root that continues its route into the sciatic nerve. About 13% to 40% of all people will suffer from sciatica at least once during their lifetime [1]. Sciatica can have severe socio-economic effects; patients are immobilised by the pain they experience and therefore cannot go to work or participate in social events.

Most cases resolve spontaneously with conservative therapy using only standard analgesics and/or physiotherapy. In a large RCT it was demonstrated that outcome of conservative and surgical therapy was comparable after 26 weeks [2]. 40% of patients randomized to the conservative care group crossed over and was treated surgically, with a mean delay of 15 weeks. With this knowledge the guidelines for surgical treatment of sciatica were adjusted and it is nowadays usual care to offer surgery only after at least 8 weeks of conservative care and preferably after 14-16 weeks of conservative care. This decision is made together with the patient in a process of Shared Decision making [3,4].

Although this treatment regimen has been demonstrated to be efficacious and cost effective, the burden for a patient during these weeks of conservative care is usually high. We seek to find a type of conservative care to reduce the discomfort due to the pain and to enable the patient to remain physically active. Not only will this add to the quality of life of the patient, but it will also prevent the patient from taking a sick-leave.

Rationale for this study

We would like to explore the effectivity of the transforaminal epidural injection (TEI) with analgesic and anti-inflammatory medication to relieve the symptoms. Theoretically, such an injection would have a painkilling effect within the first two weeks after injection, and this effect may last for months, but we know that some patients do not experience this beneficial effect [5]. Some patients report initial pain reduction but report a re-arousal of pain after several hours, days or weeks [6].

There has been extensive research on TEI, but these studies generally include patients with chronic sciatica or a mixed population of patients with acute and chronic symptoms. We performed a systematic review on TEI specifically in the acute phase and it occurred that we could find only one article on the efficacy of epidural injections administered to patients with acute sciatica (<8 weeks of symptoms) [6]. This study, conducted by Spijker et al., randomized 63 patients with a duration of symptoms of at least 2 weeks and a maximum of 4 weeks. Patients were divided over an intervention group (receiving TEI with triamcinolone) and a control group (usual care with non-iv medication). It was demonstrated that

functionality and pain relief in the back were more beneficial in the group that received an injection, but that differences were (too) small. However, the analysis of the effect was averaged over all patients in the treatment group. It is known that there is a group of non-responders after TEI, averaging 33% of patients [5]. If the outcome values of all patients are averaged, no effect will be retrieved, while there could be a clear effect for the responders. In the study of Joswig [5] recruiting 63 patients with radicular pain in the leg, 66% of patients responded well to TEI within hours after the injection and in the first 14 days after injection the VAS leg pain remained around 30 mm on a 100 mm scale. In the non-responders the VAS pain was on average 55 mm and persisted on that level for at least 14 days.

Not only was in Spijker's study no distinction made between responders and non-responders, the injection was lacking a painkilling component, like xylocaine. Moreover, the baseline values for VAS leg pain, VAS back pain and Roland Disability score were lower (better) in the control group, and the group of patients evaluated was relatively small. It appears that there is only little literature on TEI in the acute phase of sciatica and therefore additional research is obligatory.

Furthermore, it is not yet understood why some patients experience more pain than other patients. From literature it is known that pain score does not correlate with the size of the herniated lumbar disk, but there are indications that degree of infection is related [7]. It has been demonstrated that at the site of the herniated disc several inflammatory cytokines can be found leading to prostaglandin synthesis and macrophage recruitment [8-9]. For this reason, disc material will be retrieved from patients undergoing lumbar surgery during this study and histological analysis will be performed.

2. OBJECTIVES

Primary study objective:

To study effectivity of the epidural injection with analgesic and anti-inflammatory medication to relieve the symptoms within two weeks follow up.

It will be evaluated what the average leg pain score is in both treatment arms at two weeks follow up. It will be evaluated how long the effect lasts.

The leg pain and functionality at 4 weeks after randomization will also be evaluated to get informed on the responsiveness on TEI in a somewhat later stage.

Secondary study objectives:

To evaluate the outcome of TEI in the first two weeks after randomization as a predictor of NRS leg pain at 14-16 and ca 26 weeks after onset of leg pain.

Ideally, responsiveness to TEI can predict the clinical condition at 14-16 weeks after onset of sciatica. The hypothesis is that being non-responsive to TEI within two weeks, predicts an unsatisfactory condition after 14-16 weeks of suffering. This is the category of patients that in contemporary care in the Netherlands will be offered a surgical intervention. If our hypothesis is correct, in the future, this population of patients can be offered a surgical intervention at an earlier time point.

The ca 26-week time point is chosen since in the Sciatica trial [2], both the conservative and the surgical group demonstrated comparable outcome data.

Patients in this study are included while suffering from severe leg pain for 3-8 weeks.

Presumably most patients will enter the study with 4-6 weeks of leg pain. This means that on average 10 weeks after randomization, the 14-16 week leg pain time point is reached. This means that 21 weeks after randomization the ca 26-week leg pain time point is reached.

The response in NRS leg pain, ODI and patient satisfaction at 1 week after injection and at 2 weeks after injection will be correlated to the value of these parameters at 10 and 21 weeks after randomisation.

To evaluate the cost-effectivity of analgesic/anti-inflammatory epidural injections to relieve symptoms of early sciatica.

A substantial portion of the patients in this study will eventually have an MRI of the lumbar spine. These MRIs will be evaluated according to our standard MRI evaluation protocol, that has been proven to generate additional successful conclusions and subsequent publications in the past [10-15]. Protruding disc, disc and vertebral end plate changes (MODIC) will be correlated to clinical data.

A portion of the patients in this study will eventually be operated. Disc material from these patients will be evaluated for the presence (and type) of macrophages and these data will be correlated to MRI and clinical data. These additional outcome measures can be combined with the research lines on etiology of sciatica that are executed in the Neurosurgery Department of the LUMC [16].

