6.1.2 Secondary study parameters/endpoints

Sciatica is not only characterized by pain in the leg, but also by discomfort in functioning. Therefore the following parameters will also be evaluated.

NRS back pain: The pain intensity in the leg and the back will be measured with a 10-point horizontal Numeric Rating Scale (NRS), ranging from 0 (no pain) to 10 (worst imaginable pain). During each visit the NRS leg pain and NRS back pain will be scored. The patient is not entitled to see the pain scores indicated during previous visit(s). The NRS scores will be measured at baseline and at 1, 2, 4, 10 and 21 weeks after randomization.

Oswestry Disability Index (ODI): The functionality of the patient with a focus on walking and daily activities will be measured with the Oswestry Disability Index that is usually measured for sciatica complaints. The scale ranges from 0 (no disability) to 50 (worst disability possible). During each visit the ODI will be scored. The patient is not entitled to see the scores indicated during previous visit(s). The ODI scores will be measured at baseline and at 1, 2, 4, 10 and 21 weeks after randomization.

EuroQoL (EQ-5D): The EuroQoL (five point EQ-5D) will be used for the cost utility analysis. The tool measures five dimensions: mobility, self-care, daily activities, pain/discomfort, and anxiety/depression. Each dimension consists of one item, while three levels are distinguished (no problems, some problems, many problems). Use of the EuroQoL needs to be registered

(euroqol.org). The EuroQol scores will be measured at baseline and at 2, 10 and 21 weeks after randomization.

Quality of Life VAS (Health state utility VAS): To represent the patients perspective, utility will also be estimated using a VAS for the valuation of the patient's health state (ranging from 0 = as bad as death to 100 = perfect health), measured at baseline and at 2, 10 and 21 weeks after randomization.

Likert perceived recovery patient: To measure the perceived recovery a seven-point Likert scale will be used. The score on this scale varies from 'completely recovered' to 'worse than ever'. The Likert scores will be measured at baseline and at 1, 2, 4, 10 and 21 weeks after randomization.

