8. STATISTICAL ANALYSIS

8.1 Primary study parameter(s)

The study data will be analysed according to the intention-to –treat principle. The mean NRS for leg pain will be compared between the two groups using the unpaired t-test. This will also be done at the 4-week time point.

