8.2 Secondary study parameter(s)

The absolute decline in NRS leg pain, NRS back pain and ODI and increase in EQ5D from baseline to 2 weeks after randomization will be calculated using t-tests. The same will be done for the baseline to 4 weeks after randomization time point (using t-tests).

Perceived recovery Likert data will be dichotomized (1 and 2 is success, 3-7 is no success) and compared at 2 and 4 weeks after randomization or injection and to 14 and 26 weeks after start of severe leg pain using Chi-square tests.

The 2-week success data will be correlated to the success data after 14 weeks and subsequently for 26 weeks using Chi-square tests to make predictions. Logistic regression analysis will be used to correlate 2-week (and 4-week) success data to the absolute data for NRS leg pain, NRS back pain, ODI, increase in EQ5D at 14 and 26 weeks.

Cost effectiveness analysis:

The economic evaluation will consist of a cost-effectiveness analysis from a healthcare perspective (CEA: costs per extra patient with symptom relieve, i.e. the primary outcome measure) and a cost-utility analysis from a societal perspective (CUA: costs per QALY). Both analyses will be trial-based, using patient reports, with a half-year time horizon. Healthcare use will be valued according to the Dutch guidelines. QALYs will be calculated as the area under the utility curve, estimated using the Dutch tariff for the EQ-5D. As sensitivity analysis, QALYs will also be calculated using the VAS for quality of life (with power transformation). Average costs and patient outcome will be compared according to intention-to-treat, using net-benefit analysis, and using multiple imputation to account for missing data.

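### Section 8 plans no between-arm analysis of leg pain, back pain or ODI after week 4, so the duration question and the Summary's 10- and 21-week responder endpoint have no specified analysis

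*Combined protocol and SAP*

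**What the plan says.** **What is promised.** Section 2, under the primary objective: "It will be evaluated how long the effect lasts". The next sentence adds an evaluation at 4 weeks. The Summary goes further. Its objective concerns long-term relief of leg pain after injection compared with conservative care, and its main parameter is the percentage below 4 on NRS leg pain at 2, 10 and 21 weeks in each arm.

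**What is collected.** Section 6.1.1: "The NRS scores will be measured at baseline and at 1, 2, 4, 10 and 21 weeks after randomization". Section 6.1.2 repeats this for NRS back pain and says of disability: "The ODI scores will be measured at baseline and at 1, 2, 4, 10 and 21 weeks after randomization". Section 6.3 applies the schedule to both arms.

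**What is analysed.** Section 8.1: "The mean NRS for leg pain will be compared between the two groups using the unpaired t-test", at 2 weeks according to 6.1.1, and then "This will also be done at the 4-week time point". Section 8.2 takes the fall in NRS leg pain, NRS back pain and ODI together with the "increase in EQ5D from baseline to 2 weeks after randomization will be calculated using t-tests", and repeats this for week 4. Perceived recovery on the Likert scale, dichotomised, is tested by chi-square at weeks 2 and 4 and again at 14 and 26 weeks counted from the onset of severe pain. The later NRS and ODI scores appear in 8.2 only as values to be related to success at 2 or 4 weeks.

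**The concern.** The objectives ask how long a difference between the arms persists, and the schedule collects the scores needed to answer. The analysis section stops comparing the arms on those scores at week 4. The Summary's late responder endpoint is not picked up in section 8 at all.

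Two things are at stake. First, a team that follows section 8 literally would finish a 21-week trial without a between-arm result for pain or function beyond the first month, although section 1 suggests that the effect may continue for months. Second, the trial is open-label and its outcomes are self-reported. If the late scale (mean NRS, NRS below 4, ODI), the visit and the method are chosen once data are in hand, readers cannot rule out selective reporting.

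**Working it through.** **1. The plan's own figure.** Inputs from section 4.4: difference 1.5 NRS points, SD 2.6, power 90%, significance level 5% (sidedness not stated; two-sided reproduces the result).

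n per arm = 2 × (1.960 + 1.2816)² × 2.6² / 1.5² = 2 × 10.508 × 6.76 / 2.25 = 63.1, rounded up to 64. Total 128; with 10% loss, 128 / 0.9 = 142.2, against 142 stated. The sample size stands. It was set for the week-2 comparison only.

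**2. Schedule against analysis.** Section 8.2 does not say outright that its change-score t-tests and the Likert comparison are between arms; I read both that way. Section 2 equates 10 weeks after randomisation with about 14–16 weeks of pain, and 21 weeks with about 26, so the times counted from onset in 8.2 are taken as the week-10 and week-21 questionnaires.

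| Outcome | Follow-up collected (weeks) | Between-arm analysis in section 8 |
|---|---|---|
| NRS leg pain, mean | 1, 2, 4, 10, 21 | 2 and 4 (8.1; change in 8.2) |
| NRS back pain | 1, 2, 4, 10, 21 | 2 and 4 (change in 8.2) |
| ODI | 1, 2, 4, 10, 21 | 2 and 4 (change in 8.2) |
| NRS leg pain below 4 (Summary: 2, 10, 21) | follows from NRS | none stated |
| Likert recovery, dichotomised | 1, 2, 4, 10, 21 | 2, 4, and about 10 and 21 |
| Costs and QALYs | diaries at 10 and 21; EQ-5D at 2, 10, 21 | half-year economic evaluation |

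Both visits after week 4, that is 2 of the 5 follow-up visits, have no between-arm analysis of pain or function.

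**3. Could another planned analysis stand in?** The prediction analysis relates early success to later scores. That is prognosis and contains no contrast of the arms. The histology analysis in 8.3 uses NRS leg pain and ODI at all time points, but only for patients whose disc tissue was taken at surgery. Neither estimates a late treatment difference.

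**4. Would late estimates be informative?** Assume that 64 per arm are evaluable and that the SD of 2.6 still holds at the later visits; section 4.4 gives both figures for week 2 only.

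- Standard error = 2.6 × √(2/64) = 0.460
- 95% CI half-width = 1.96 × 0.460 = 0.90 NRS points
- SD 2.0: 1.96 × 2.0 × √(2/64) = 0.69
- SD 3.2: 1.96 × 3.2 × √(2/64) = 1.11

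All are below the 1.5 points that section 4.4 calls clinically relevant. On the same assumptions, two-sided 5% power at a single visit is 90% for a difference of 1.5 points, but 58% for 1.0 point. A late interval that includes zero would therefore not show that a smaller effect has gone.

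**5. Why estimates and not five tests.** Five separate tests at 5% would give a familywise error of 1 − 0.95⁵ = 0.226 if independent. Visits in the same patients are correlated, so this is an approximation.

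**The case against.** The strongest reply is that late comparisons are not absent from the document. The Summary names a responder percentage at 10 and 21 weeks in both arms, Likert recovery is compared at those times, and the economic evaluation covers half a year by intention to treat. This is correct, and it limits the point. A reader might infer that the duration question cannot be answered, or that every late pain result would be post hoc. The documents support neither. The data are collected in both arms, and the responder percentage is named in advance. What the Summary lacks is an analysis in section 8. A dichotomised recovery item does not show how long a difference in leg pain lasts. QALYs accumulate over time and do not show when a pain difference ends. The cost-effectiveness analysis counts relieved patients without naming a visit.

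A second reply is that the duration sentence in section 2 is followed at once by the 4-week evaluation, so that week 4 may be all that was meant. The wording permits this, but the Summary's long-term objective and its 10- and 21-week endpoint do not fit it.

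A reader might also count week 1 as a broken promise and speak of three visits out of five. Section 2 uses week 1 only as a predictor and promises no comparison of arms then. Including it in the model is convenient, not owed.

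The last objection stands. Sections 3 and 6.3 allow surgery in either arm after the first two weeks, and section 3 allows repeat injections in the treatment arm. Section 1 reports that 40% of the conservative arm of an earlier trial crossed over to surgery. A late difference by allocated arm therefore compares strategies and cannot isolate how long one injection acts. This governs how the late estimates are described; it is no reason to leave them unspecified.

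**Conclusion.** The point holds as a gap in the analysis section. Section 8 specifies no between-arm analysis of NRS leg pain, NRS back pain or ODI after week 4, and none at any visit for the responder endpoint in the Summary. The primary week-2 comparison and the sample size are unaffected. The gap covers both late visits for three outcomes, one of them the main outcome. If the week-2 planning figures carry over, each late NRS difference could be estimated to within about 0.90 points, or 0.69 to 1.11 for SD 2.0 to 3.2. The finding rests on reading the 8.2 tests as between-arm and on the mapping of time from onset to the questionnaires. It should be settled before the data are analysed.

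**What to change.** Add to section 8.2:

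- **Scores.** One linear mixed model each for NRS leg pain, NRS back pain and ODI, with arm, visit (1, 2, 4, 10, 21 weeks), arm-by-visit interaction and baseline score, and all randomised patients in their allocated arm. Report the between-arm difference with 95% CI at each visit as secondary estimates. Answer the duration question mainly from weeks 2, 4, 10 and 21. These estimates replace the change-score t-tests in 8.2 for these three outcomes.
- **Responders.** A between-arm comparison of the percentage with NRS leg pain below 4 at 2, 10 and 21 weeks, so that section 8 agrees with the Summary.
- **Hierarchy.** The week-2 comparison in 8.1 remains the single primary test. The model's own week-2 estimate is secondary.
- **Interpretation.** State that late estimates compare the allocated strategies, including any surgery or repeat injections, and not the isolated pharmacological duration of one injection. Report the frequency of both by arm.

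Cost: new wording and some extra analysis, with no added patients, visits or data. Mixed models are already named in 8.3, though only for histology. The downside is a set of secondary estimates without multiplicity control, which the report must say.
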